8.4.7 REPORTING EVENTS TO PARTICIPANTS

n/a

8.4.8 EVENTS OF SPECIAL INTEREST

n/a

8.4.9 REPORTING OF PREGNANCY

Pregnancy, although not itself a serious adverse event, should also be reported on a serious adverse event form or pregnancy form and be followed up to determine outcome, including spontaneous or voluntary termination, details of birth, and the presence or absence of any birth defects or congenital abnormalities.

8.5 UNANTICIPATED PROBLEMS

8.5.1 DEFINITION OF UNANTICIPATED PROBLEMS (UP)

The Office for Human Research Protections (OHRP) considers unanticipated problems involving risks to participants or others to include, in general, any incident, experience, or outcome that meets all of the following criteria:

- Unexpected in terms of nature, severity, or frequency given (a) the research procedures that are described in the protocol-related documents, such as the Institutional Review Board (IRB)-approved research protocol and informed consent document; and (b) the characteristics of the participant population being studied;
- Related or possibly related to participation in the research (“possibly related” means there is a reasonable possibility that the incident, experience, or outcome may have been caused by the procedures involved in the research); and
- Suggests that the research places participants or others at a greater risk of harm (including physical, psychological, economic, or social harm) than was previously known or recognized.

8.5.2 UNANTICIPATED PROBLEM REPORTING

The investigator will report unanticipated problems (UPs) to the reviewing Institutional Review Board (IRB) and to the Protocol Monitoring Committee (PMC) of the institution. The UP report will include the following information:

- Protocol identifying information: protocol title and number, PI’s name, and the IRB project number;
- A detailed description of the event, incident, experience, or outcome;
- An explanation of the basis for determining that the event, incident, experience, or outcome represents an UP;
- A description of any changes to the protocol or other corrective actions that have been taken or are proposed in response to the UP.

To satisfy the requirement for prompt reporting, UPs will be reported using the following timeline:

- UPs that are serious adverse events (SAEs) will be reported to the IRB and to the PMC/study sponsor within 24 hours of the investigator becoming aware of the event.
- Any other UP will be reported to the IRB and to the PMC/study sponsor within 24 hours of the investigator becoming aware of the problem.
- All UPs should be reported to appropriate institutional officials (as required by an institution’s written reporting procedures), the supporting agency head (or designee), and the Office for Human Research Protections (OHRP) within 24 hours of the IRB’s receipt of the report of the problem from the investigator.

8.5.3 REPORTING UNANTICIPATED PROBLEMS TO PARTICIPANTS

n/a

9 STATISTICAL CONSIDERATIONS

9.1 STATISTICAL HYPOTHESES

For the primary endpoint, the optimal two-stage design to test the null hypothesis that $P_0 \leq 0.10$ versus the alternative that $P_1 \geq 0.40$.

9.2 SAMPLE SIZE DETERMINATION

For the primary endpoint, the optimal two-stage design to test the null hypothesis that $P_0 \leq 0.10$ versus the alternative that $P_1 \geq 0.40$ has an expected sample size of 8.93 and a probability of early termination of 0.813. If the treatment is actually not effective, there is a 0.031 probability of concluding that it is (the target for this value was 0.050). If the treatment is actually effective, there is a 0.198 probability of concluding that it is not (the target for this value was 0.200). After testing the treatment on 8 patients in the first stage, the trial will be terminated if 1 or fewer responds. If the trial goes on to the second stage, a total of 13 patients will be studied. If the total number responding is less than or equal to 3, the treatment is rejected.

9.3 POPULATIONS FOR ANALYSES

The analysis datasets (e.g., which participants will be included in each analysis) include the following:

- Intention-to-Treat (ITT) Analysis Dataset
- Safety Analysis Dataset: defines the subset of participants for whom safety analyses will be conducted (e.g., participants who took at least one dose of study intervention)
- Per-Protocol Analysis Dataset: defines a subset of the participants in the full analysis (ITT) set who complied with the protocol sufficiently to ensure that these data would be likely to represent the effects of study intervention according to the underlying scientific model (e.g., participants who took at least 80% of study intervention for 80% of the days within the maintenance period)

9.4 STATISTICAL ANALYSES

9.4.1 GENERAL APPROACH

For the primary endpoint, we will use the Simon's two stage approach as described in detail above in the Sample Size Determination Section. For the secondary endpoints we will use descriptive statistics as well as the Kaplan-Meier approach for the time to event endpoints.

All analyses will be performed in either SAS v. 9.4 or R software using standard procedures and packages.

9.4.2 ANALYSIS OF THE PRIMARY EFFICACY ENDPOINT(S)

Our primary endpoint for this analysis will be confirmed overall response rate (ORR) in injected lesions based on modified RECIST criteria appropriate for cutaneous neoplasms (ORR = complete response + partial response)

According to the Simon's two-stage design, after testing the treatment on 8 patients in the first stage, the trial will be terminated if 1 or fewer responds. If the trial goes on to the second stage, a total of 13 patients will be studied. If the total number responding is less than or equal to 3, the treatment is rejected. Please see Sample Size description above for further details.

In addition, we will construct a 95% exact confidence interval for the ORR.

9.4.3 ANALYSIS OF THE SECONDARY ENDPOINT(S)

For all secondary endpoints except those with time-to-event responses, we will use basic descriptive statistics such as the mean, median, standard deviation and range for continuous variables and frequencies for categorical variables. We will construct exact 95% confidence intervals to describe these secondary endpoints.

For time-to-event responses, we will use Kaplan-Meier estimates and plots to describe the endpoints. Response duration is measured from the time of first injection to initial partial response or complete response. Progression free survival is measured from time of first injection to progression of disease or appearance of new CA, not present at the time of study entry. The median progression-free survival will be reported with 95% confidence interval.

All secondary endpoints are for descriptive purposes, and no power analyses have been performed for them.

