1 PROTOCOL SUMMARY

1.1 SYNOPSIS

Title: A phase II study of talimogene laherparepvec (T-VEC) in the treatment of recurrent cutaneous angiosarcoma

Study Description: Seventy-five percent of cutaneous angiosarcoma (CA) patients will eventually fail systemic therapy, and relapsed/refractory patients are left with no known efficacious treatment options. We hypothesize that direct treatment of CA lesions with T-VEC will stimulate local antitumor response, leading to objective responses and prevention of recurrence among enough patients to make this a viable treatment option for the affected population.

Objectives:

Primary Objective: To evaluate the efficacy of T-VEC as treatment for relapsed/refractory cutaneous angiosarcoma

Secondary Objectives:

1. To establish duration of response among treated patients that demonstrate response
2. To measure the duration of progression-free survival among treated patients
3. To measure the complete response rate for lesions that have complete clinical regression following study treatment
4. To monitor adverse events following administration of T-VEC injections
5. To measure the rate of patients requiring surgical resection of T-VEC–treated lesions

Tertiary/Exploratory Objectives:

1. To measure the degree of immune infiltration in surgically resected T-VEC–treated tumors
2. To evaluate surgical outcomes for those patients whose T-VEC–treated tumors are resected

Endpoints:

Primary Endpoint: Overall response rate: the proportion of patients to demonstrate complete or partial responses in injected lesions per modified RECIST criteria appropriate for cutaneous neoplasms.

Secondary Endpoints:

1. Response duration will be measured from the time of initial partial response or complete response until documented progression

2. Progression-free survival: period from time of first injection to progression of disease or appearance of new cutaneous angiosarcoma tumors that were not present at the time of study entry
3. Complete Response rate: proportion of patients with CR, defined as lesions with complete clinical regression
4. Incidence of adverse events from injection of T-VEC into cutaneous angiosarcoma
5. Proportion of patients whose T-VEC–treated tumors require surgical resection

Tertiary/Exploratory Endpoints:

1. Immunohistochemistry and flow cytometry analyses of immune infiltration within resected tumor specimens

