3 OBJECTIVES AND ENDPOINTS

Table 2: Objectives and Endpoints

OBJECTIVES	ENDPOINTS
Primary	
To evaluate the efficacy of T-VEC as treatment for relapsed/refractory cutaneous angiosarcoma	Overall response rate (ORR): the proportion of patients to demonstrate complete or partial responses in injected lesions per modified RECIST criteria appropriate for cutaneous neoplasms at 24 weeks.
Secondary	
1. To establish duration of response among treated patients	1. Response duration will be measured from the time of initial partial response or complete response until documented progression
2. To measure the rate of progression-free survival among treated patients	2. Progression-free survival: period from time of first injection to progression of disease or appearance of new CA tumors that were not present at the time of study entry
3. To measure the complete response (CR) rate for lesions that have complete clinical regression following study treatment	3. Complete Response rate: proportion of patients with pCR, defined as lesions with complete clinical regression
4. To monitor adverse events following administration of T-VEC injections	4. Incidence of adverse events from injection of T-VEC into cutaneous angiosarcoma
5. To measure the rate of patients requiring surgical resection of T-VEC–treated lesions	5. Proportion of patients whose T-VEC–treated tumors require surgical resection
6. To measure the degree of immune infiltration in surgically resected T-VEC–treated tumors	6. Immunohistochemistry and flow cytometry analyses of immune infiltration within resected tumor specimens
Tertiary/Exploratory	
1. To measure the degree of immune infiltration in surgically resected T-VEC–treated tumors	1. Immunohistochemistry and flow cytometry analyses of immune infiltration within resected tumor specimens to determine patterns of lymphocyte infiltration associated with response
2. To evaluate surgical outcomes for those patients whose T-VEC–treated tumors are resected	Surgical outcomes recorded will include margin status, percent viable tumor, postoperative complications, and disease-free interval following resection.

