8.1.2.4 DURATION OF RESPONSE

Duration of Response

Duration of overall response: The duration of overall response is measured from the time measurement criteria are met for CR or PR (whichever is first recorded) until the first date that recurrent or progressive disease is objectively documented (taking as reference for progressive disease the smallest measurements recorded since the treatment started).

The duration of overall CR is measured from the time measurement criteria are first met for CR until the first date that progressive disease is objectively documented.

Duration of stable disease: Stable disease is measured from the start of the treatment until the criteria for progression are met, taking as reference the smallest measurements recorded since the treatment started, including the baseline measurements.

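### Section 9.4.3 defines response duration as time to response, contradicting the synopsis, Table 2 and section 8.1.2.4, so the analysis as written cannot show how long responses last

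*Combined protocol and SAP*

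**What the plan says.** Section 9.4.3 assigns Kaplan-Meier estimates and plots to the time-to-event secondary endpoints and then defines this one: "Response duration is measured from the time of first injection to initial partial response or complete response". Section 9.4.1 mentions only the "Kaplan-Meier approach for the time to event endpoints" and gives no start or end event.

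Three other places define the same endpoint differently:

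- Synopsis (1.1), secondary endpoint 1: "Response duration will be measured from the time of initial partial response or complete response until documented progression".
- Table 2 (section 3), secondary endpoint 1: the same wording as the synopsis.
- Section 8.1.2.4: the clock starts when the criteria for CR or PR are first met and runs "until the first date that recurrent or progressive disease is objectively documented".

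The objective is also worded in two ways. The synopsis has "To establish duration of response among treated patients that demonstrate response"; Table 2 has "To establish duration of response among treated patients". Section 9.4.3 names no population for the endpoint.

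Section 9.4.3 also limits the weight of these analyses: "All secondary endpoints are for descriptive purposes, and no power analyses have been performed for them".

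**The concern.** An interval from first injection to first response measures how fast patients respond. It contains no time after the response, so it cannot show whether the response lasts. The two quantities also read in opposite directions: a long duration of response is favourable, while a long time to response means slow onset.

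The plan itself treats time to response as a separate quantity. Section 2.3.2 reports it for the earlier combination study, with a median of 16 weeks and a range of 8 to 32.

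At stake is secondary objective 1. A programmer working from section 9 would produce a time-to-response curve labelled response duration. Progression-free survival would not fill the gap, because it starts at first injection and is not limited to responders.

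**Working it through.** **The plan's own figures.** The plan states no number for response duration. Its computable design figures are those of the two-stage design in 9.2 (8 patients, stop at 1 or fewer responses; 13 patients, reject the treatment at 3 or fewer). Exact binomial calculation gives:

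| Quantity | Stated | Recomputed |
|---|---|---|
| Type I error at 10% | 0.031 | 0.0307 |
| Type II error at 40% | 0.198 | 1 − 0.8015 = 0.1985 |
| Early termination at 10% | 0.813 | 0.8131 |
| Expected sample size at 10% | 8.93 | 8 + 5 × (1 − 0.8131) = 8.93 |

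These agree to within 0.001. Response duration does not enter them, so nothing here changes them.

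**Definitions side by side.**

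| Place | Clock starts | Clock stops |
|---|---|---|
| Synopsis; Table 2 | First PR or CR | Documented progression |
| 8.1.2.4 | First CR or PR | Documented recurrence or progression |
| 9.4.3 | First injection | First PR or CR |

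The stop event in 9.4.3 is the start event everywhere else, so the two intervals share no follow-up time.

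**Illustration (assumed data).** The plan gives no response times for monotherapy. Assume 5 responders (0.40 × 13 = 5.2) with first response at weeks 8, 12, 16, 24 and 32. These dates were chosen to fit the median and range quoted in 2.3.2 for the combination study.

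*Under 9.4.3, responders only.* Every responder has the event, so nobody is censored. The Kaplan-Meier curve steps to 0.8, 0.6, 0.4, 0.2 and 0 at weeks 8, 12, 16, 24 and 32. It first falls to 0.5 or below at week 16, so the median is 16 weeks. No progression date is used.

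*Under 8.1.2.4.* Let every response last d weeks:

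| Assumed d | Progression falls at weeks | Median under 9.4.3 | Median under 8.1.2.4 |
|---|---|---|---|
| 4 | 12 to 36 | 16 | 4 |
| 36 | 44 to 68 | 16 | 36 |

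A ninefold change in durability (36/4) leaves the 9.4.3 result unchanged.

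**Population.** Suppose 9.4.3 were applied to all 13 treated patients, with 8 non-responders. If they are all censored at week 52, the curve levels off at 8/13 = 0.62 and has no median. If they are all censored at week 10, it is 12/13 = 0.923 at week 8, 0.923 × 3/4 = 0.692 at week 12 and 0.692 × 2/3 = 0.462 at week 16, so the median is 16 weeks. The output depends on who is included and when they are censored, and in neither case does a responder's progression count.

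**The case against.** The strongest reply is that this is a slip in one sentence. Three of four definitions agree, one of them sits under the efficacy analyses heading (8.1.2), and the label in 9.4.3 is still response duration. A careful analyst would probably notice. That lowers the likelihood of harm, but 9.4.3 is the text that governs the analysis and nothing else in section 9 corrects it. Choosing between definitions once data are available would weaken prespecification.

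A second reply is that the population question resolves itself. If the clock starts at first response, a non-responder has no start date and cannot enter. This is right for the synopsis, Table 2 and 8.1.2.4. The ambiguity has consequences only under the 9.4.3 interval, so it is a by-product of the same error. Aligning the Table 2 objective is tidying.

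A third reply concerns the illustration. Very long responses might not be observable: a response lasting 104 weeks from the assumed dates would end at weeks 112 to 136, after follow-up closes under 8.1.2.6. That is why only the 4- and 36-week cases are used, and they are enough. Likewise, the missing median in the 13-patient example depends on the week-52 censoring, as the week-10 alternative shows.

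**Conclusion.** The concern holds. Section 9.4.3 states an analysis rule that contradicts the plan's other three definitions, and following it would give a time-to-response estimate under the name of response duration. The contradiction rests on the text alone; only the size of the effect uses assumed response dates and durations.

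The reach is limited. The endpoint is descriptive and unpowered, the primary test, stopping boundaries and sample size are unaffected, and the data collected can still answer the objective under the 8.1.2.4 definition. It should be fixed, but it does not threaten the trial's main conclusion.

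**What to change.** Replace the sentence in 9.4.3 with wording to this effect:

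> Among patients with CR or PR, response duration runs from the date the criteria for CR or PR are first satisfied to the first objectively documented recurrence or progression. Patients without such an event are censored at their last disease assessment.

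Then settle these points:

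- Word the Table 2 objective like the synopsis, so that it refers to responders.
- The censoring rule above is an addition, since none of the four definitions gives one. State whether a telephone recurrence check counts as a disease assessment.
- State whether responders here are the confirmed responders of the primary analysis (9.4.2).
- None of the four definitions counts death as an event. If it should count, change the synopsis, Table 2, 8.1.2.4 and 9.4.3 together.
- If the present 9.4.3 interval is wanted, report it separately as time to response.

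The cost is a short edit to 9.4.3 and to one objective in Table 2, with no new visits.

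One limit remains. Lesions are measured every 2 weeks during treatment, but afterwards recurrence need be checked only at a minimum of every 6 months (8.1.1; Table 1, footnote e), so late progression and censoring dates may be coarse. The end of follow-up also differs. Section 8.1.1 counts 2 years from the off-study visit, which for a patient treated 52 weeks is about 52 + 4 + 104 = week 160. Section 8.1.2.6 counts 2 years from the start of injections, week 104. This separate inconsistency should be reconciled, because it sets how long a response can be observed.

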7 STUDY INTERVENTION DISCONTINUATION AND PARTICIPANT DISCONTINUATION/WITHDRAWAL

7.1 DISCONTINUATION OF STUDY INTERVENTION

Discontinuation from T-VEC does not mean discontinuation from the study, and remaining study procedures should be completed as indicated by the study protocol. If a clinically significant finding is identified (including, but not limited to changes from baseline) after enrollment, the investigator or qualified designee will determine if any change in participant management is needed. Any new clinically relevant finding within 4 weeks of last T-VEC injection will be reported as an adverse event (AE).

In the absence of treatment delays due to adverse events, treatment may continue for 12 months or until one of the following criteria apply:

1. Complete response with no cutaneous angiosarcoma to inject
2. Disease progression as per section 8.1.2.3
3. Deterioration in performance status precluding further treatment
4. G4/5 adverse events persisting ≥ 2 weeks
5. Patient decides to withdraw from the study, or
6. PI decision

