8.1.2.3 RESPONSE CRITERIA

Evaluation of Target Lesions

Complete Response (CR): Disappearance of all target lesions.

Partial Response (PR): At least a 30% decrease in the sum of the diameters of target lesions, taking as reference the baseline sum diameters.

Progressive Disease (PD): At least a 20% increase in the sum of the diameters of target lesions, taking as reference the smallest sum on study (this includes the baseline sum if that is the smallest on study). (Note: the appearance of one or more new lesions is also considered progression).

Stable Disease (SD): Neither sufficient shrinkage to qualify for PR nor sufficient increase to qualify for PD, taking as reference the smallest sum diameters while on study.

Evaluation of Non-Target Lesions

Complete Response (CR): Disappearance of all non-target lesions and normalization of tumor marker level.

Progressive Disease (PD): Appearance of one or more new lesions and/or unequivocal progression of existing non-target lesions. Unequivocal progression should not normally trump target lesion status. It must be representative of overall disease status change, not a single lesion increase.

Although a clear progression of “non-target” lesions only is exceptional, the opinion of the treating physician should prevail in such circumstances, and the progression status should be confirmed at a later time by the review panel (or Principal Investigator). Photography of these changes is recommended.

Evaluation of Best Overall Response

The best overall response is the best response recorded from the start of the treatment until disease progression/recurrence (taking as reference for progressive disease the smallest measurements recorded since the treatment started). The patient's best response assignment will depend on the achievement of both measurement and confirmation criteria.

Overall Response Criteria

Target Lesions	Non-Target Lesions	New Lesions	Overall Response	Best Overall Response when Confirmation is Required
CR	CR	No	CR	≥ 4 wk Confirmation
CR	Non-CR/Non-PD	No	PR	≥ 4 wk Confirmation
CR	Not evaluated	No	PR	
PR	Non-CR/Non-PD/not evaluated	No	PR	
SD	Non-CR/Non-PD/not evaluated	No	SD	Documented at least once ≥ 4 wk from baseline
PD	Any	Yes or No	PD	No prior SD, PR, or CR
Any	PD***	Yes or No	PD	
Any	Any	Yes	PD	

*** In exceptional circumstances, unequivocal progression in non-target lesions may be accepted as disease progression.

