Note: Patients with a global deterioration of health status requiring discontinuation of treatment without objective evidence of disease progression at that time should be reported as “symptomatic deterioration.” Every effort should be made to document the objective progression even after discontinuation of treatment.

Objective response—Response and progression will be evaluated in this study using a primary endpoint of objective response, which is defined as either complete or partial response

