8.1.2.5 PROGRESSION-FREE SURVIVAL

Progression-free survival is defined as the duration of time from start of treatment to time of progression or death, whichever comes first.

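### Progression-free survival has two event rules: the synopsis, Table 2 and section 9.4.3 leave out death, section 8.1.2.5 counts it, and nothing says which governs the reported median

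*Combined protocol and SAP*

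**What the plan says.** Four places define progression-free survival (PFS).

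- Synopsis (1.1), secondary endpoint 2: "period from time of first injection to progression of disease or appearance of new cutaneous angiosarcoma tumors".
- Table 2 (section 3), secondary endpoint 2: "period from time of first injection to progression of disease or appearance of new CA tumors".
- Section 9.4.3, the analysis section: "Progression free survival is measured from time of first injection to progression of disease or appearance of new CA".
- Section 8.1.2.5, the section headed for this endpoint: "duration of time from start of treatment to time of progression or death, whichever comes first".

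Section 9.4.3 plans Kaplan-Meier estimates and then commits to a summary: "The median progression-free survival will be reported with 95% confidence interval". It also states that secondary endpoints are descriptive and unpowered. It gives no date at which a patient without an event is censored and does not refer to 8.1.2.5.

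**The concern.** The first three definitions name progression and new lesions only. The fourth names progression or death. A patient who dies without documented progression is an event under 8.1.2.5. Under the other three the death is simply not addressed: it is neither counted nor assigned a censoring date. Read literally, 9.4.3 yields time to progression, a different quantity from PFS.

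At stake are the promised median and its 95% confidence interval. In an open-label single-arm trial of at most 13 patients, one reclassified patient can move either of them, and with two written rules available the choice could be made after the data are seen.

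**Working it through.** **Is death the only difference?**

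- *Start point.* Three places start at first injection and one at start of treatment. T-VEC is given alone, so these are the same day.
- *New lesions.* Section 8.1.2.5 does not list them, but section 8.1.2.3 says "the appearance of one or more new lesions is also considered progression", so they are covered.
- *Death.* Counted in 8.1.2.5, absent from the other three. This is the one substantive difference.

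**Can such a death occur and be seen?** Eligibility excludes visceral and CNS metastases, and lesions are measured every 2 weeks on treatment (8.1.2), so the number may be small or zero. It need not be zero: the note in 8.1.2.3 foresees patients who stop for deterioration without objective progression, and long-term contact is every six months (8.1.1, 8.1.2.6). Vital status is followed for up to 2 years, so the death would be known and would have to be classified.

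**The plan's own figures.** None exists for PFS: no assumed median, event count or power. The figures in 9.2 concern response only. With stage 1 stopping at 1 or fewer of 8 and rejection of the treatment at 3 or fewer of 13, exact binomial calculation gives type I error 0.0307 (stated 0.031), type II error 1 − 0.8015 = 0.1985 (stated 0.198), early termination 0.8131 (stated 0.813) and expected size 8.934 (stated 8.93). They reproduce to rounding and do not involve PFS.

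**Illustration (all inputs assumed except the maximum of 13).** All 13 patients have an event under 8.1.2.5 at distinct times; exactly one event, at rank *j*, is a death without documented progression. The median is the first time with S(t) ≤ 0.5.

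*Death counted.* S after rank *k* is (13 − *k*)/13. At *k* = 6 it is 7/13 = 0.538; at *k* = 7 it is 6/13 = 0.462. The median is rank 7.

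*(a) Death not counted, censored on its date.* For *k* > *j*, S = [(14 − *j*)/13] × [(13 − *k*)/(13 − *j*)].

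- *j* = 1: at *k* = 7, S = 6/12 = 0.5. Median unchanged.
- *j* = 2: at *k* = 7, S = (12/13)(6/11) = 0.503, above 0.5. Median moves to rank 8.
- *j* = 3 to 6: S at *k* = 7 is higher still, reaching (8/13)(6/7) = 0.527 at *j* = 6. Median at rank 8.
- *j* = 7: rank 7 is no longer an event; at *k* = 8, S = (7/13)(5/6) = 0.449. Median at rank 8.
- *j* = 8 to 13: the curve up to rank 7 is untouched. Median unchanged.

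Result: unchanged in 7 of 13 placements, one event time later in 6.

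*Confidence interval in (a).* With the log-log Greenwood interval and the death counted, the lower bound for S first falls to 0.5 or below at rank 3 (0.512 at rank 2, 0.442 at rank 3). The upper bound does so at rank 10 (0.554 at rank 9, 0.475 at rank 10). The interval is ranks 3 to 10. With the death censored, the upper limit becomes rank 11 for *j* = 1 to 10 and stays at rank 10 for *j* = 11 to 13. The median or a limit therefore changes in 10 placements; in 4 of them (*j* = 1, 8, 9, 10) only the upper limit moves.

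*(b) Death not counted, censored at an earlier last assessment.* Let *c* be the number of events before the censoring, *c* = 0 to *j* − 1. There are 1 + 2 + … + 13 = 91 combinations.

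- *c* = 0: 12 patients remain and S reaches 0.5 at the sixth counted event. That is rank 6 if *j* ≥ 7 (7 combinations, one earlier) and rank 7 if *j* ≤ 6 (6 unchanged).
- *c* ≥ 1: the median is the seventh counted event. That is rank 8 if *j* ≤ 7 (1 + 2 + … + 6 = 21 later) and rank 7 if *j* ≥ 8 (7 + 8 + … + 12 = 57 unchanged).

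Result: 6 + 57 = 63 unchanged, 21 later, 7 earlier.

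*Sensitivity.* If S = 0.5 is resolved by the midpoint, (a) gives 6 unchanged, 1 half a rank later and 6 one rank later; (b) gives 58 unchanged, 6 half a rank later, 21 one rank later and 6 half a rank earlier. If the trial stops at 8 patients, the reference median is rank 4, and (a) gives 4 of 8 unchanged and 4 of 8 one event time later.

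**The case against.** The best case against is that this is an omission, not a conflict. Section 8.1.2.5 is the only section devoted to the endpoint and the only one worded as a formal definition; the other three could be read as shorter restatements, with 8.1.2.5 supplying the missing event, as the word survival in the name suggests. That reading is reasonable but inferred. Section 9.4.3 spells out its own start and events immediately before promising the median. Nor can it be assumed to defer to section 8: its description of response duration, from first injection to initial response, also departs from 8.1.2.4.

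A second objection is that such deaths will be rare. The plan does try to capture progression: "Every effort should be made to document the objective progression even after discontinuation of treatment", and "Discontinuation from T-VEC does not mean discontinuation from the study, and remaining study procedures should be completed". Section 8.1.1 also allows clinical assessment, not only telephone contact, in long-term follow-up. This stands as a limit on size, not as an answer to which rule applies.

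Third, the endpoint is descriptive, has no comparator or decision rule, and the illustration is hypothetical. All true. The earlier-median cases in (b) are also remote: they need a death at rank 7 or later in a patient whose last assessment preceded the first event in the whole trial.

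**Conclusion.** The concern holds. Three definitions omit death, one counts it, and nothing in the document settles which is pre-specified. Followed literally, 9.4.3 labels time to progression as PFS.

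The size cannot be fixed from the document. It is nil if no patient dies without documented progression. With one such death among 13 patients who all have events, the median shifts by at most one event time, and the direction depends on a censoring date that the plan does not give: unchanged or later if censored at death, occasionally earlier if censored at a previous assessment. The placement counts treat every rank alike and are not likelihoods. The primary response analysis is unaffected. This should be fixed before analysis, but it does not threaten the trial's main conclusion.

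**What to change.** Use one event rule in the synopsis, Table 2 and 9.4.3, matching 8.1.2.5. Suggested wording: *time from first injection to first documented progression, including new cutaneous angiosarcoma lesions, or death from any cause, whichever is earlier*. Add one sentence to 9.4.3 giving the censoring date for patients without an event; the last tumor assessment is one option, offered here as a suggestion because the document states none.

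If death is meant to be left out, rename the endpoint time to progression in those three places, state in 9.4.3 the date at which deaths are censored, and reconcile 8.1.2.5.

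For the first option the cost is wording in three places plus one sentence. Vital status is already collected, so no new data, visits or patients are needed. Counting deaths may give a less favorable median; in the remote cases under (b) it would give a later one.
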